3. STUDY DESIGN

3.1. GENERAL SCHEMA

This is a Phase I, randomized, double-blind study designed to evaluate the safety, tolerability, and PK of inhaled MBS-COV in healthy adult participants in the part A and part B of the study. A total of 44 male and female healthy participants will be enrolled. All participants, after signing the Informed Consent Form (ICF), will be assessed during the screening phase. Only those participants who successfully complete the screening phase and meet the study eligibility criteria will be enrolled. MBS-COV will be administered via inhalation through a portable nebulizer.

Part A (SAD phase)

Part A is randomized, blinded study of a single ascending dose (SAD) phase to evaluate the safety, tolerability and PK of inhaled MBS-COV in healthy participants.

All participants will have a screening visit within 28 days of check-in (Day -1) to determine eligibility. Eligible participants will be admitted to the study center on study Day -1 at which point their eligibility to participate in the study will be confirmed. Only those participants who successfully complete the screening phase and meet the study eligibility criteria will proceed to be randomized to receive a single dose of MBS-COV or placebo in the morning of Day 1 at the assigned dose.

Participants will be assigned to one of up to three doses of MBS-COV (0.3 mg/kg, 0.6 mg/kg, 1.2 mg/kg) to be treated sequentially with increasing doses. Each cohort will include eight (8) participants (6 active and 2 placebo) per below table:

Table 3-1: SAD Phase Cohorts

Cohort		Number of Participants	MBS-COV Dose (mg/kg)	Frequency of Dose
SAD Phase	A1	6 (MBS-COV) +2 (placebo)	0.3	Single Administration
	A2	6 (MBS-COV) +2 (placebo)	0.6	Single Administration
	A3	6 (MBS-COV) +2 (placebo)	1.2	Single Administration

SAD phase will include a sentinel design in which two (2) participants at the given cohort dose be initially enrolled. If the dose can be well tolerated for 48 hours after full administration per site Principle Investigator's judgement, the remaining 6 participants will be enrolled to receive a single dose of MBS-COV at the same dose.

The decision for cohort (dose level) escalation to the higher dose levels will be made by the study SRC after safety review of available information 7-day post treatment period. The data from SAD phase will be reviewed for safety trends to start MAD phase.

Part B (MAD Phase)

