This is a randomized, double-blind, placebo-controlled study in approximately 20 healthy participants. Doses will be selected based on a comprehensive review of SAD data and estimates of the clinically efficacious dose.

The MAD Phase of the study consists of a screening period followed by multiple dose administrations of MBS-COV or placebo through a portable nebulizer once daily for 7 consecutive days (Day 1 to Day 7). Participants will be followed up for 21 days to assess post-treatment safety.

The decision for the escalation to the higher dose levels will be made by the study SRC after safety review of available information 7-day post treatment period. Each cohort will include ten participants (8 active and 2 placebo) per table below:

Table 3-2: MAD Phase Cohorts

Cohort		Number of Participants	MBS-COV Dose (mg/kg)	Dose
MAD Phase	B1	8 (MBS-COV) +2 (placebo)	0.6	Once daily for 7 days
	B2	8 (MBS-COV) +2 (placebo)	1.2	Once daily for 7 days

Study Visits:

- **Screening Visit (SV: Up to 28 Days prior to Day 1):** Consists of signing the ICF and study qualification based on evaluation of inclusion/exclusion criteria.
- **Treatment Visit 0 (T0: Day -1):** All participants continuing to meet eligibility criteria will be enrolled into the study and confined to research clinic until Day 2 for cohort A1 to A3 (SAD phase) and Day 9 for cohort B1 to B2 (MAD phase).
- **Treatment Visit 1: Baseline Visit (T1: Day 1):** The first assigned study treatment dose will be administered after completion of all study evaluations. Adverse events and changes in concomitant medications will be collected. Participants in Cohorts A1 to A3 will inhaled a single dose of MBS-COV or placebo through a portable nebulizer on Day 1. Participants in cohort B1 and B2 will receive doses of MBS-COV or placebo by through a portable nebulizer once daily for 7 consecutive days from Day 1 to Day 7.

Part A (SAD Phase)

- **Treatment Visit 2 (T2: Day 2)**
- **Treatment Visit 3 (T3: Day 3)**
- **Treatment Visit 4 (T4: Day 4)**
- **Treatment Visit 5 (End of Treatment) (T5: Day 7)**

- **Follow-Up Visit 1 (FU1: Day 14)**
- **Follow-Up Visit 2 (FU2: Day 28)**

Part B (MAD Phase)

- **Treatment Visit 2 (T2: Day 2)**
- **Treatment Visit 3 (T3: Day 3)**
- **Treatment Visit 4 (T4: Day 4)**
- **Treatment Visit 5 (T5: Day 5)**
- **Treatment Visit 6 (T6: Day 6)**
- **Treatment Visit 7 (T7: Day 7)**
- **Treatment Visit 8 (T8: Day 8)**
- **Treatment Visit 8 (End of Treatment) (T9: Day 9)**

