- **Follow-Up Visit 1 (FU1: Day 14)**
- **Follow-Up Visit 2 (FU2: Day 28)**

If any of the dose escalation stopping criteria have occurred in Part A or Part B, the SRC will make a final recommendation for dose escalation to the next cohort.

- **NOTE:** The dose escalation decision through the study will not be made until the following:
 - (1) All study participants in a given cohort have been enrolled,
 - (2) All such participants have completed Treatment Visit 5 (Day 7) (for SAD-Part A) and Treatment Visit 9 (Day 9) (for MAD-Part B) of the study or withdrawn from the study, whichever occurs first,
 - (3) The SRC will review the available safety data and recommend further dose escalation.

[figure not shown]
Additionally, dose escalation stopping criteria are defined per the below:

- a. Death in any participant in which the cause of death is judged to be possibly, probably or definitely related to MBS-COV.
- b. The occurrence in any participant of a severe local application site reaction (Grade 3 which doesn't resolve or recurs, or Grade 4) that is judged to be possibly, probably or definitely related to MBS-COV.
- c. The occurrence in any participant of a SAE whose causal relationship to MBS-COV is judged to be probably, possibly, or definitely related to MBS-COV.
- d. The occurrence, in two or more participants of Grade 3 AE or laboratory abnormalities, judged to be probably, possibly, or definitely related to MBS-COV.

- e. The occurrence of two of the same AE or laboratory abnormality \geq Grade 3 judged to be probably, possibly, or definitely related to receipt of MBS-COV
- f. The occurrence, in one or more participants of Grade 4 AE or laboratory abnormalities, judged to be probably, possibly, or definitely related to receipt of MBS-COV.
- g. Any pattern of significant symptoms, physical findings, or laboratory abnormalities that, although individually minor, collectively represent a safety concern in the opinion of the investigator and are judged by the SRC to be at least possibly related to MBS-COV.
- h. PK exposure limits of mean AUC of 385.6 h*ng/mL or C_{max} of 141.8 ng/mL for one cohort, whichever comes first.(Single dose: AUC of 386.9 h*ng/mL or C_{max} of 91.7 ng/mL).

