The SRC will review the PK data (if applicable) and safety trends of available information 7-day post treatment period of Cohort A1 and A2 (or if study stops prematurely due to safety reasons), to start part B of the study. The starting dose of Part B will be determined by SRC.

Figure 3-1: Dose Escalation Scheme

Blood Sample Collection for the PK study:

- SAD cohorts A1 to A3:** For the single dose on day 1, blood samples will be collected before dosing, and afterwards at 5 min (± 1 min), 15 min (± 2 min), 0.5 h (± 5 min), 1 h (± 5 min), 2 h (± 5 min), 4 h (± 5 min), 8 h (± 10 min), 10 h (± 10 min), 24 h (± 10 min) and 48 h (± 10 min) (Total 11 samples) after dosing.
- MAD cohort B1 and B2:** Blood samples will be collected on Day 1 and Day 7 before dosing, and afterwards at 5 min (± 1 min), 15min (± 2 min), 0.5 h (± 5 min), 1 h (± 5 min), 2 h (± 5 min), 4 h (± 5 min), 8 h (± 10 min), 10 h (± 10 min) on Day 1; and at 5 min (± 1 min), 15min (± 2 min), 0.5 h (± 5 min), 1 h (± 5 min), 2 h (± 5 min), 4 h (± 5 min), 8 h (± 10 min) on Day 7.

10 min), 10 h (\pm 10 min), 24 h (\pm 10 min) and 48 h (\pm 10 min) after dosing on Day 7; and before dosing on Day 2 to Day 6 (Total 25 samples). The detailed study schedule and assessments in each visit are provided in [Section 4](#) of the protocol.

Blood Sample Collection for the immunogenicity study:

- Blood Sample will be collected on Day 1 before dosing, Day 14 and Day 28 for SAD and MAD cohorts, and the analysis will be performed when analytic method is well-established.

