8.5. BLINDING AND PREVENTION OF BIAS

8.6. INTERIM ANALYSIS

There is no efficacy interim analysis planned for this study; however, the safety data from all participants of each completed cohort will be reviewed by the SRC prior to enrolment of further participants or dose escalation.

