3.1. Part A: SAD phase

Part A includes 3 dose-escalation cohorts (0.3 mg/kg, 0.6 mg/kg, 1.2 mg/kg MBS-COV or placebo). Each cohort will include 8 participants (6 active and 2 placebo) per below table:

| Cohort | MBS-COV Does Active:placebo | Frequency of Does |
|--------|--------------------------------|-----------------------|
| A1 | 0.3 mg/kg (6:2) | Single Administration |
| A2 | 0.6 mg/kg (6:2) | Single Administration |
| A3 | 1.2 mg/kg (6:2) | Single Administration |

From the perspective of safety, sentinel dosing will be used in each cohort, and the first 2 subjects in each cohort will be randomized 1:1 to MBS-COV or placebo. If the dose can be well tolerated for 48 hours after full administration per the study Safety Review Committee (SRC) consisting of the sponsor (designee), site Principle Investigator, and medical monitor, the remaining 6 subjects in the cohort may be randomized 5:1 to MBS-COV or placebo.

All participants will have a screening visit within 28 days of check-in (Day -1) to determine eligibility. Eligible participants will be admitted to the study center on study Day -1 at which point their eligibility to participate in the study will be confirmed. Only those participants who successfully complete the screening phase and meet the study eligibility criteria will proceed to be randomized to receive a single dose of MBS-COV or placebo in the morning of Day 1 at the assigned dose.

The decision for cohort (dose level) escalation to the higher dose levels will be made by the study SRC after safety review of available information 7-day post treatment period. The data from SAD phase will be reviewed for safety trends to start MAD phase.

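### No visible sentence requires A3 (single dose, 1.2 mg/kg) to be cleared before B2 gives 1.2 mg/kg daily for 7 days, or caps the Part B dose at the highest cleared single dose

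*Protocol*

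**What the plan says.** **Opening Part B.** The Protocol (synopsis and section 3.1) has the SRC review PK data, where applicable, and "safety trends of available information 7-day post treatment period of Cohort A1 and A2". It adds: "The starting dose of Part B will be determined by SRC". A3 is not named.

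**Escalating within a part.** The note in section 3.1 holds back each decision until everyone in the given cohort is enrolled and "All such participants have completed Treatment Visit 5 (Day 7) (for SAD-Part A) and Treatment Visit 9 (Day 9) (for MAD-Part B"), or has withdrawn. For B2 the given cohort is B1.

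**Sentinels.** Section 3.1 states: "SAD phase will include a sentinel design in which two (2) participants at the given cohort dose be initially enrolled". The other six follow if the dose is tolerated for 48 hours. SAP section 3.1 adds that "the first 2 subjects in each cohort will be randomized 1:1 to MBS-COV or placebo". Neither Protocol section 3.1 under Part B nor SAP section 3.2 describes such a step for Part B.

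**Broader statements.** Section 3.1 also says "The data from SAD phase will be reviewed for safety trends to start MAD phase" and, for Part B, "Doses will be selected based on a comprehensive review of SAD data and estimates of the clinically efficacious dose". Section 1.6 places Part B after a sufficient Part A result. Section 8.6 says "the safety data from all participants of each completed cohort will be reviewed by the SRC" before further enrolment or escalation.

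**The concern.** A3 and B2 share the dose of 1.2 mg/kg. A3 gives it once, starting with two sentinels (one active, by the SAP) who are watched for 48 hours, and ends in a Day 7 review. B2 gives it on seven consecutive days to 8 active participants, with no stagger described. In a first-in-human study in healthy participants, one expects the single-dose result at a level to be in hand before repeat dosing at that level. The visible text leaves that order to the SRC's judgement and gives it no written dose ceiling for Part B.

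At stake is one specific path: A1 and A2 cleared, B1 reviewed, the planned doses kept, and A3 incomplete or never run. On that path the first people to inhale 1.2 mg/kg could be the B2 participants.

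**Working it through.** **1. Does any visible sentence tie B2 to A3?**

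| Protocol statement | What it requires | Does it make B2 wait for A3? |
|---|---|---|
| 3.1, opening of Part B | SRC review of A1 and A2 | No; A3 is not named |
| 3.1, escalation note | Completion of the given cohort (B1, Day 9) | No |
| 3.1, SAD data reviewed to start MAD | A review of SAD data | No; cohorts not specified, and it concerns the start of Part B |
| 3.1, Part B dose selection | A comprehensive review of SAD data | No; does not name A3, require all SAD cohorts or set a ceiling |
| 1.6 | A sufficient Part A result | No; sufficient is not defined |
| 8.6 | Review of each completed cohort | Only if A3 is complete |
| 3.1, escalation stopping criteria in either part | Referral to the SRC | Only if A3 has been dosed and a criterion is met |

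The last two rows protect participants when A3 has produced data. No row covers an A3 that is still running or was not run.

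**2. What would be cleared when B2 starts?** Inputs are Protocol Tables 3-1 and 3-2.

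- Dose ratio with A2 the highest cleared single dose: 1.2 / 0.6 = 2.
- Active participants with SRC-cleared data at 1.2 mg/kg: 0 if A3 is not cleared, 6 if it is.
- Nominal cumulative dose: A3 1 × 1.2 = 1.2 mg/kg; B1 7 × 0.6 = 4.2 mg/kg; B2 7 × 1.2 = 8.4 mg/kg.

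B2 would therefore not start without human data. Its 8 active B1 predecessors would each have received 4.2 mg/kg over a week, though never more than 0.6 mg/kg in a day.

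**3. The protocol's own safety margins (section 1.6).** Pulmonary deposition is taken as 10% in the hamster and 100% in humans.

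- Hamster deposited dose: 87.9 × 0.1 = 8.79 mg/kg/day.
- Systemic margin at 1.2 mg/kg: 8.79 × 0.13 / 1.2 = 0.952, as stated.
- Systemic margin at 0.6 mg/kg: 8.79 × 0.13 / 0.6 = 1.90.
- Local margin at 1.2 mg/kg: 1.51 / 0.072 = 20.97, as stated.

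The step from 0.6 to 1.2 mg/kg takes the systemic margin from above 1 to just below 1 under these deposition assumptions, while the local margin stays large.

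**4. How long would B2 wait for A3?** Assume that A3 and B1 start on the same calendar day and that the other six in A3 are dosed at 48 hours.

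- A3: sentinels on day 1, the rest on day 3, their Day 7 on calendar day 3 + 6 = 9.
- B1: Day 9 on calendar day 9. Wait: 9 − 9 = 0 days.
- With the ±1 day visit windows (Tables 4-1 and 4-2): A3 at the latest on day 10, B1 at the earliest on day 8. Wait: at most 10 − 8 = 2 days.
- Section 3.1 also speaks of information from the 7 days after treatment. For B1, last dosed on Day 7, that could mean Day 14. A3 would then be ready 14 − 9 = 5 days earlier.
- Each day that A3 starts after B1 adds one day to the difference.

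**The case against.** **The figures may settle it.** Figures 0-1 and 3-1 are the escalation schematics, and cohort order is what such figures show. They were not visible in the text examined. This objection stands: the point concerns the written text, and the sponsor should be asked to confirm the order.

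**The A1 and A2 sentence does another job.** It governs the start of Part B. The planned start is B1 at 0.6 mg/kg, the dose A2 tests. This also stands. The sentence is sound for B1; what is missing is a matching condition for B2.

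**The SRC would know about a bad A3.** A reader might infer that the plan lets B2 proceed in the face of a failed A3. The documents do not support that. A stopping event in either part goes to the SRC, and section 8.6 has it review every completed cohort. Nor does any document give a reason for A3 to lag behind B1.

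**B2 is closely watched, and the step is ordinary.** Vital signs and ECG are taken three times on each dosing day, spirometry at 5, 15, 30 and 60 minutes, and participants stay in the unit to Day 9. Doubling matches the Part A steps. This reduces the concern. It does not replace the sentinel step, because such monitoring detects harm only after exposure has begun, in up to 8 active participants.

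**The 0.952 margin.** A reader might infer that the protocol concedes 1.2 mg/kg to be unsafe. It does not. The figure assumes full deposition in humans against 10% in the hamster. The NOAEL is also the top dose of a 14-day daily study, and the local margin is 20.97. Section 1.6 accepts the dose on the ground that preclinical work showed no systemic toxicity that could not be monitored.

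**Conclusion.** The point holds for the written text. Part B opens on A1 and A2, B2 follows B1, and no visible sentence makes B2 wait for A3 or limits the Part B dose to the highest cleared single dose. The gap is confined to an A3 still running or not run when B2 is approved. In that case B2 receives daily twice the highest cleared single dose, with 0 instead of 6 active participants cleared at 1.2 mg/kg.

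This rests on the planned doses being kept and on the figures not already showing the order. The SRC's discretion could prevent the outcome, so this is a change the sponsor should make to turn discretion into a rule. It is not evidence that B2 is planned ahead of A3. Confidence is medium because of the unseen figures. No analysis result is affected.

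**What to change.** Add to the Protocol, in the synopsis and section 3.1, after the sentence on the Part B starting dose:

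> No Part B daily dose may exceed the highest single dose whose Part A cohort has completed Day 7 and been cleared by the SRC; B2 (1.2 mg/kg daily) starts only after A3 is cleared.

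If the figures already show this order, the sentence only puts it in words. The SAP analysis needs no change.

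The cost is one sentence in two places, with no added participants, visits or procedures. B1 at 0.6 mg/kg is unaffected once A2 is cleared. With a same-day start of A3 and B1, B2 waits 0 to 2 days beyond B1 Day 9; a later A3 delays it day for day. The real downside is that B2 may have to be lowered or not opened if A3 is not cleared, which would cost the repeat-dose data at 1.2 mg/kg.

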3.2. STUDY CENTER

One study center in the United States (US).

3.3. STUDY POPULATION

The target population for this study will be healthy participants.

3.4. ELIGIBILITY CRITERIA

3.4.1. Inclusion Criteria

Participants will be eligible for enrollment in the study only if they meet ALL the following criteria at time of Screening:

1. Male or female adults who are between 18 and 55 years old (inclusive).
2. Body mass index (BMI) between 18.0 and 32.0 kg/m² (inclusive).
3. No serious or chronic underlying disease which would adversely affect the study conduct and data interpretation per the Investigator.
4. Female participants should have negative results in serum pregnancy test at screening and negative urine pregnancy test at admission (Day -1).
5. Participants with normal spirometry (FEV1 %: 80 % or greater) results at screening or day -1.
6. Both male and female participants and their partners of childbearing potential must agree to use two medically accepted methods of contraception (e.g., barrier contraceptives [male condom, female condom, or diaphragm with a spermicidal gel], hormonal contraceptives [implants, injectables, combination oral contraceptives, transdermal patches, or contraceptive rings], or one of the following methods of birth control (intrauterine devices, tubal sterilization or vasectomy) or must practice complete abstinence from intercourse of reproductive potential from study entry to 3 months after the last day of treatment (excluding women who are not of childbearing potential and men who have been sterilized).

7. Participants should have normal (or abnormal but not clinically significant) laboratory results per the PI's judgement including the hematology, biochemistry, coagulation indices and urinalysis.
8. Participants should have a normal (or abnormal but not clinically significant) 12-lead ECG at screening and day -1 and chest X-ray at screening.
9. Participants should be willing to cooperate and able to participate in this study, comply with all protocol requirements, and sign an informed consent.
10. Current non-smokers and those who have not smoked within the last 3 months. This includes the use of cigarettes, e-cigarettes, and nicotine replacement products.
11. Nasopharyngeal or nasal swab sample of Participants collected for COVID-19 antigen rapid test at screening and qRT-PCR test on Day -1 should be negative.

3.4.2. Exclusion Criteria

Participants meeting ANY of the following criteria at time of Screening will be excluded from enrollment:

1. The participant has a known history of, or a positive test result for, hepatitis B surface antigen (HBsAg), hepatitis C virus (HCV), or human immunodeficiency virus (HIV) at screening.
2. As reported by the participant has severe cardiovascular disease, neurological disease, hematological disease, infectious disease, mental disorder, liver disease, gastrointestinal disease, lung disease, endocrine disease, immune disease or kidney disease, or has a history of the above diseases, or other symptoms known to interfere with the absorption, distribution, metabolism, or excretion of the medicine, or other conditions that the Investigator believes will increase the risk of the participant and might interfere with the study conduct and results interpretation.
3. The participant has history or presence of active lung disease (i.e., asthma, chronic obstructive pulmonary disease [COPD], pulmonary fibrosis, hemoptysis, bronchiectasis) or prior intubation due to respiratory failure conditions.
4. The participant has upper respiratory infection within the 3 months prior to the first dose of study drug.
5. Consumed more than 14 units of alcohol per week in the 6 months before screening (1 unit of alcohol = 360 mL of beer or 45 mL of spirits with 40% alcohol content or 150 mL of wine) or have taken alcohol products in the 48 hours prior to administration, or those who have a positive alcohol breath test result at screening and day -1.
6. Unwillingness to abstain from the consumption of any caffeine or alcohol-containing food or drinks that may influence the drug metabolism from 48 hours before administration.

7. History of drug abuse or a positive drug abuse (barbiturates, methamphetamine, benzodiazepines, morphine/opiates, phencyclidine (PCP), amphetamines, tetrahydrocannabinol (THC), methylenedioxymethamphetamine (MDMA), cocaine, methadone, and cotinine) test result at screening and day -1.
8. Female participants who are lactating.
9. Use of prescription or non-prescription drugs, including vaccine within 14 days or 5 half-lives (whichever is longer) prior to the first dose of study drug.
10. The participant has received an experimental agent (vaccine, drug, biologic, device, blood product or medication) within 1 month prior to the first dose of study drug and will receive another experimental agent during the duration of this study.
11. The participant has a history of frequent nose bleeding.
12. Participants with known allergic reactions to the study drug or its excipients.
13. The participant has an acute sinusitis or history of chronic sinusitis, a history of active allergic rhinitis (AR), history of perennial allergic rhinitis (PAR), or current seasonal allergic rhinitis (SAR), or recent viral rhinitis within 2 weeks prior to administration.
14. The participant has Any nasopharyngeal abnormality that may have interfered with nasal absorption, distribution, or study-related evaluations of signs or symptoms (e.g., polyps, septal deviation).
15. Blood donation of more than 400 mL within 3 months before screening or more than 200 mL within 4 weeks before screening or plan to donate blood during study period.
16. Any other clinical condition that, in the Investigator's judgment, would potentially compromise study compliance or the ability to evaluate safety/efficacy.

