- [1] Informed consent must be obtained prior to participation in any protocol-related activities that are not part of routine care.
- [2] Initial evaluation of participant eligibility will be performed by Investigator.
- [3] Medical history and current therapies (medications and non-medications).
- [4] Symptom-directed physical examination.
- [5] Vital signs will include blood pressure, pulse, respiration rate, and temperature. On treatment visits will be conducted three times a day, within 120 minutes before administration, within 1 hour after administration, and 4-6 hours after administration, respectively. On other visits will be conducted once during the visit.
- [6] 12-lead ECG on treatment visits will be conducted three times a day, within 120 minutes before administration, within 1 hour after administration, and 4-6 hours after administration, respectively. On other visits will be conducted once during the visit.
- [7] Spirometry assessments will be started 5 minutes after the dosing with frequent spirometry measurements at 5 (± 1 min), 15 (± 1 min), 30 (± 5 min), 60 minutes (± 5 min). On other visits will be conducted once during the visit. If spirometry is completed within 7 days prior to dosing, this assessment does not need to be repeated on Day-1.
- [8] Participants will be discharge from the clinic when all required assessments for T3 Day (3) are performed.
- [9] If hematology, biochemistry, coagulation and urinalysis are completed within 7 days prior to dosing, this assessment does not need to be repeated on Day-1.
- [10] Hematology
Hemoglobin, Hematocrit (HCT), Red Blood Cells (RBC), White Blood Cells (WBC) with total and differential count, Absolute Neutrophil Count (ANC) and platelets.
- [11] Biochemistry
Hepatic function indicators: total bilirubin, alkaline phosphatase, aspartate aminotransferase (AST), alanine aminotransferase (ALT), total protein, albumin, Lactate dehydrogenase (LDH), amylase and lipase

Renal function indicators: Serum creatinine, eGFR

Electrolytes: sodium, potassium, chloride, calcium and bicarbonate

Other: glucose (random), triglyceride (TG), cholesterol (total), Creatine kinase.

[12] Coagulation

Prothrombin time (PT), activated partial thromboplastin time (APTT), thrombin time (TT), fibrinogen (FIB)

[13] Serum pregnancy test in screening visit (Will include FSH and estradiol levels at screening for post-menopausal women only) and EOT, and Urine pregnancy test in other visits.

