4.2.2. Part A (SAD) - Treatment Visit 0 (T0: Day -1)

If continued to be eligible for the study at Treatment Visit 0 per below, the participant will proceed to be enrolled into Part A (SAD) of the study in next visit.

- Assessment of continued eligibility
- Medical history
- Vital signs
- 12-lead ECG

- List concomitant medications
- Spirometry assessment
- Participant confined to research clinic
- Laboratory assessments (hematology, chemistry, coagulation and urine analysis, urine drug screening and alcohol screen)
- Urine pregnancy test
- Nasopharyngeal or nasal swab for COVID-19

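### Inclusion 5 gives an abnormal Day -1 spirometry repeat no effect on eligibility, and exclusion 7 is ambiguous about a drug or cotinine test that is positive at one visit only

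*Protocol*

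**What the plan says.** **Spirometry.** Protocol Section 3.4.1, inclusion 5, and the synopsis ask for "Participants with normal spirometry (FEV1 %: 80 % or greater) results at screening or day -1". Table 4-1, footnote 7, adds a waiver: "If spirometry is completed within 7 days prior to dosing, this assessment does not need to be repeated on Day-1". Sections 4.2.1 (Part A) and 4.3.2 (Part B) repeat it.

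**Drug and alcohol tests.** In Section 3.4.2, exclusion 7 ends "cocaine, methadone, and cotinine) test result at screening and day -1". Exclusion 5 has a breath-test limb, "or those who have a positive alcohol breath test result at screening and day -1", and a separate limb for those who "have taken alcohol products in the 48 hours prior to administration".

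**Criteria that do use the Day -1 result.** Inclusion 8 asks for an acceptable "12-lead ECG at screening and day -1 and chest X-ray at screening". Inclusion 11 ends "COVID-19 antigen rapid test at screening and qRT-PCR test on Day -1 should be negative". Inclusion 4 requires a negative pregnancy test at screening and again at admission.

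**The Day -1 check.** Tables 4-1 and 4-2 place spirometry, drug and alcohol screening and an eligibility evaluation on Day -1. Sections 4.2.2 and 4.3.2 list "Assessment of continued eligibility" at that visit. Section 7.2 refers the assessment of continued eligibility back to the criteria in Sections 3.4.1 and 3.4.2, and the lead-in to each of those lists ties the criteria to the screening time point.

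**Use of the data.** Change in spirometry, to assess acute bronchospasm, is one of the primary safety outcomes (protocol Section 2.2.1; SAP Sections 4.1.1 and 4.2.1). SAP Section 7.1 takes as baseline the last effective record before the first dose.

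**The concern.** The same connector works differently in an inclusion and in an exclusion. In inclusion 8, *and* means that both ECGs must be acceptable, so a failure on Day -1 disqualifies. In an exclusion, *and* literally means that both tests must be positive before anyone is excluded. In inclusion 5, *or* means that one normal result is enough.

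This is a first-in-human study of an inhaled product. Section 7.11 says that spirometry is used to make sure participants have no undiagnosed respiratory disease. A rule that requires a repeat test shortly before dosing and then gives its result no weight does not serve that purpose. It could also admit a participant with low pre-dose FEV1 to a small cohort whose safety data inform dose escalation.

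**Working it through.** The plan states no figure on this point, so the check is one of logic. Let *s* = 1 if the screening result is abnormal and *d* = 1 if the Day -1 result is abnormal, with both tests done.

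**Step 1. The rules.**
- Inclusion 5, literal: eligible if *s* = 0 or *d* = 0. If every result counted: eligible only if *s* = 0 and *d* = 0.
- Exclusion 7, literal: excluded if *s* = 1 and *d* = 1. If either visit counted: excluded if *s* = 1 or *d* = 1.
- Exclusion 5: excluded if (*s* = 1 and *d* = 1), or if alcohol was taken in the 48 hours before dosing. Assumption: a positive Day -1 breath test means alcohol within 48 hours of the Day 1 dose. With no other intake in that window, the rule reduces to excluded if *d* = 1.

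**Step 2. The four patterns.**

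| *s* | *d* | Inclusion 5, literal | Inclusion 5, every result | Exclusion 7, literal | Exclusion 7, either visit | Exclusion 5, breath limb only | Exclusion 5, with 48-hour limb |
|---|---|---|---|---|---|---|---|
| 0 | 0 | eligible | eligible | not excluded | not excluded | not excluded | not excluded |
| 0 | 1 | **eligible** | not eligible | **not excluded** | excluded | not excluded | excluded |
| 1 | 0 | eligible | not eligible | not excluded | excluded | not excluded | **not excluded** |
| 1 | 1 | not eligible | not eligible | excluded | excluded | excluded | excluded |

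In the row that matters most (normal at screening, abnormal on Day -1), the literal wording lets the participant through for spirometry and for the drug and cotinine test, but not for alcohol. That is 2 of 3 criteria. For alcohol, the open case is a positive test at screening only.

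**Step 3. When two spirometry results can disagree.** Screening may fall up to 28 days before Day 1. If the screening test was within 7 days of dosing, no repeat is needed, and a single result settles inclusion 5. If it was more than 7 days before dosing, the schedule requires the repeat. Only then does *or* decide the matter, and it lets the older normal result qualify a participant whose newer result is below 80%. The Day -1 eligibility check does not change this, because Section 7.2 applies the same criteria.

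**Step 4. Baseline.** Tables 4-1 and 4-2 schedule Day 1 spirometry only after dosing. A Day -1 value, where obtained, is therefore the last scheduled pre-dose record and becomes the baseline under SAP Section 7.1. This assumes that an abnormal but technically valid record counts as effective, a term the SAP does not define.

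**Step 5. Size.** One affected participant is 1/6 = 16.7% of a Part A active arm or 1/8 = 12.5% of a Part B active arm. The documents give no rate of discordant results, so these figures only restate the arm sizes.

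**The case against.** A fair defence has four parts.

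1. *At screening and day -1* may simply name the two visits at which the tests are done. The schedule supports this: screening for drugs and alcohol on Day -1, beside an eligibility evaluation, would serve little purpose if positives were ignored. Section 4.2.2 also makes progress to the next visit conditional on continued eligibility and then lists those tests. This stands for exclusions 5 and 7 and makes the point there one of ambiguity. It does not help inclusion 5, because no reading of *or* says what happens when two results disagree.
2. The *or* in inclusion 5 follows from the waiver, since a strict *and* would contradict a protocol that allows the Day -1 test to be skipped. This also stands. The connector is not simply reversed; the gap is confined to discordant results.
3. Other rules cover much of the risk. Inclusion 10 bars smoking and nicotine products within 3 months, exclusion 9 bars recent prescription and non-prescription drugs, and exclusion 16 leaves room for the investigator's judgement. These are partial backstops. Cotinine is the scheduled objective check on inclusion 10, and exclusion 16 is discretionary.
4. No sample size, analysis set or planned summary changes. This is correct.

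A reader might infer that a Day -1 alcohol result can never exclude anyone who passed at screening. The 48-hour limb of exclusion 5 contradicts that, and Section 6.2 also requires abstinence from 48 hours before dosing. A reader might also infer that the spirometry baseline is distorted. The documents do not support this: the baseline is the last pre-dose record, so change is measured from the participant's actual pre-dose state.

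**Conclusion.** The point holds in a limited form, with different strength for each criterion.

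- **Inclusion 5:** firm. A required Day -1 repeat that is abnormal has no effect on eligibility under this criterion, yet supplies the baseline for a primary safety outcome.
- **Exclusion 7:** an ambiguity whose literal reading does not exclude a participant with one positive test. It is not an established rule that positives are accepted.
- **Exclusion 5:** a small residue, namely a positive breath test at screening alone.

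The alcohol conclusion rests on the assumption in Step 1 and the baseline statement on the one in Step 4. How often results would disagree is unknown, so the 1-in-6 figure is illustrative only. The change is worth making because it is cheap and bears on entry to a first-in-human inhaled study.

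**What to change.** Reconcile the three criteria with the Day -1 tests and eligibility evaluation in Tables 4-1 and 4-2, so that every result obtained counts.

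- **Inclusion 5:** require normal spirometry *at screening and, whenever performed, at Day -1*, keeping the 7-day waiver.
- **Exclusion 7, and exclusion 5 for consistency:** a positive test *at screening or Day -1*.
- **Lead-ins to Sections 3.4.1 and 3.4.2:** reconcile the reference to the screening time point with criteria that use Day -1 results.
- **Synopsis:** mirror all changes.

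No test or visit is added, because these assessments are already scheduled at both time points. The cost is the rewording and a few more screen failures on Day -1.
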